## OBJECTIVES

The objective of this study is to assess the feasibility of utilizing endobronchial ultrasound guided miniforceps to acquire adequate amounts of tissue to perform PD-L1 testing on in patients with nonsmall cell lung cancer. Adequacy will be defined as sufficient core biopsy material to perform the PD-L1 assay specific for nivolumab.

## SPECIFIC AIMS:

To evaluate the technique of EBUS-MFB in obtaining adequate tissue to perform PD-L1 testing.

## I. BACKGROUND

Endobronchial ultrasound guided transbronchial needle aspiration (EBUS-TBNA) has significantly changed the landscape for the diagnosis and staging of lung cancer and intrathoracic malignancy. Previously, patients with suspected lung cancer required invasive surgical techniques to adequately stage disease prior to therapy. Presently, EBUS-TBNA is recommended by the American College of Chest Physicians for the diagnosis of suspected lung cancer based on the body of literature supporting the efficacy of this technique as well as its favorable safety profile compared to more invasive surgical techniques such as mediastinoscopy or thoracoscopy (Silvestri GA et al. *Chest* 2013;143:e211S-e250S).

The development of molecular profiling for lung cancer has significantly altered the treatment for this disease (NCCN Task Force Report. JNCCN 2011;9(5)). The discovery of molecular mutations such as the epidermal growth factor receptor (EGFR) have allowed targeted therapy to be given to patients with certain molecular profiles, improving quality of life as well as periods of disease free progression for certain patients with advanced stages of lung cancer.

Immune checkpoint inhibition targeting PD-L1 is therapy for patients with advanced nonsmall cell lung cancer that has become standard of care. Currently, the assay for detection of PD-L1 has only been approved for use with core biopsy specimens, and not cytologic, needle based preparations. As EBUS-TBNA is recommended as a first line procedure over surgical techniques, many patients undergoing this staging procedure will not have tissue specimens which are adequate for PD-L1 testing, and may require additional procedures to obtain core material for PD-L1 testing.

Recently, new instrumentation has become available for endobronchial ultrasound which propose to provide core biopsy specimens using this bronchoscopic approach. Endobronchial ultrasound guided miniforceps biopsies (EBUS-MFB) have been safely used to obtain larger amounts of tissue than traditionally provided by transbronchial needle aspiration. In this technique, small, 1mm forceps are placed through the working channel of the EBUS bronchoscope and are passed directly into mediastinal lymph nodes or centrally located mediastinal or hilar lesions and are used to obtain "core" biopsies of

targeted areas. EBUS-MFB has shown efficacy and safety for the diagnosis of granulomatous inflammation and lung cancer (Chen A, et al. Ann Thorac Surg 2011;92:284-289), though has not been specifically evaluated for the use of collecting material for PD-L1 testing, which is relatively new.

#### II. RESEARCH DESIGN AND METHODS

This is a single center prospective feasibility study to assess the adequacy of specimens collected using EBUS-miniforceps for performing PD-L1 testing using the nivolumab assay.

The patient population in this study is patients with advanced stage lung cancer. The protocol outlines our standard of care approach, which is to perform a full staging EBUS examination of the mediastinum and hila, starting with N3 nodes, then moving to N2 nodes and finally to N1 nodes as needed. Rapid on-site evaluation (ROSE) is utilized to give on-site feedback to the bronchoscopist so that we know if the lymph node being sampled is diagnostic on-site. If, for example, an N3 lymph node is diagnostic, then we do not need to subject the patient to additional procedural or anesthesia related risks of sampling additional lymph nodes. The information provided from the original lymph node is diagnostic and pathologically stages the patient. This is standard of care.

**Primary outcomes:** Adequacy of collected material to perform PD-L1 testing on specimens collected using EBUS-MFB using the nivolumab assay.

**Secondary outcomes:**

1. Adverse event rates and safety profile of EBUS-MFB.

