#### Bronchoscopy:

1. *Sedation:* Moderate sedation will be administered by the bronchoscopy team in a dedicated bronchoscopy suite. Patients will be continuously monitored throughout the procedure as per standards of care at Barnes-Jewish Hospital.
2. *Airway inspection:* When adequate sedation has been given, the bronchoscope (BF-P190, Olympus, Tokyo, Japan) will be inserted transorally into the tracheobronchial tree and a standard airway inspection will be performed.
3. *Convex-probe endobronchial ultrasound and transbronchial needle aspiration:* Following standard airway inspection, the convex-probe EBUS bronchoscope (BF-UC180F, Olympus, Tokyo, Japan) will be inserted transorally into the tracheobronchial tree and will be advanced to the targeted centrally located lesion. Transbronchial needle aspiration from the targeted lesion will be performed using a 22 gauge aspiration needle.
4. *Rapid on-site evaluation (ROSE):* Rapid on-site evaluation will be performed as per standard clinical care by a cytology team.
  - a. ROSE diagnostic: in cases in which ROSE yields a specific diagnosis of nonsmall cell lung cancer, EBUS-MFB will subsequently be performed.
  - b. ROSE non-diagnostic: in cases in which ROSE does not yield a specific diagnosis, additional lymph nodes that are pathologically enlarged as defined above will be targeted for EBUS-TBNA
    - i. If no additional lymph nodes are pathologically enlarged, the procedure will be terminated and EBUS-MFB will not be performed
5. *EBUS-miniforceps biopsy:* following the diagnosis of nonsmall cell lung cancer using ROSE, EBUS-MFB will be performed in the following manner:
  - a. With the EBUS bronchoscope positioned at the targeted lymph node station, 6 needle punctures will be made into the targeted lymph node using the 22 gauge aspiration needle through the EBUS bronchoscope using continuous endobronchial ultrasound guidance.
  - b. The 22 gauge aspiration needle will then be removed and 1mm miniforceps (Boston Scientific), will be passed through the working channel of the EBUS-bronchoscope into the targeted lymph node through the puncture site made using the 22 gauge needle using continuous endobronchial ultrasound guidance.
  - c. The miniforceps will be used to obtain a core biopsy of the targeted lymph node using continuous endobronchial ultrasound guidance and will be withdrawn from the EBUS bronchoscope.

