- d. 8 core biopsies will be obtained from each targeted lymph node using this technique, with each core biopsy specimen placed in formalin for PD-L1 testing.
6. Management of complications: the major complications of bronchoscopic biopsy include pneumothorax and bleeding:
  - a. Pneumothorax: a post procedure chest x ray will be performed following the bronchoscopy. Should a pneumothorax be present, it will be managed by either observation and follow up chest x-ray or by tube thoracostomy at the discretion of the bronchoscopist.
  - b. Bleeding: intra procedural bleeding will be managed using local tamponade, iced saline lavage or mechanical occlusion at the discretion of the bronchoscopist.

Post-bronchoscopy:

1. *Chest x-ray:* A routine portable chest x-ray will be performed on all patients following bronchoscopy as per standard clinical practice at Barnes-Jewish Hospital/Washington University School of Medicine to assess for pneumothorax.
2. *Recovery:* Patients will be recovered in a dedicated post-procedure area as per standard care at Barnes-Jewish Hospital/Washington University School of Medicine

Laboratory Analysis:

1. Formalin placed specimens will be sent for PD-L1 testing using the assay specific for nivolumab.

RISKS OF PROCEDURES:

The greatest risks from bronchoscopy are related to moderate or deep sedation and the very act of passing a bronchoscope into the airway. To mitigate risks of bronchoscopy all patients will be monitored by a nurse and a respiratory therapist during the procedure. In addition, oxygen saturation (using pulse oximetry) respiratory rate, blood pressure, ECG, and heart rate will be continuously monitored. Patients will not be released until they are fully awake and medically stable.

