#### DATA COLLECTION

- (1) *Feasibility:* feasibility will be determined as the ability to provide adequate specimens to perform PD-L1 testing. Any specimen in which the requested assay returns as “insufficient material to perform testing” will be deemed an “inadequate” specimen. Adequacy for PD-L1 testing will be recorded.
- (2) *Radiographic Information:* Size and location of the central pulmonary lesion will be recorded. Size will be recorded as the longest axis diameter.
- (3) *Procedural Characteristics:* Procedural information to be recorded will include procedure time, amount of sedation given, and number of biopsies performed
- (4) *Diagnostic yield:* Diagnostic yield based on final cytology and/or histopathology will be determined from the results of the bronchoscopy. A biopsy that results in a specific diagnosis, either malignant or benign, that adequately explains the clinical scenario as determined by the treating physician, will be considered truly positive. Plan for further diagnostic management for patients who have a non-diagnostic procedure will be determined by the treating physician as clinical indicated.
- (5) *Complications:* Adverse event rates will be documented. Pneumothorax will be documented by post-biopsy CXR or chest ultrasonography, and the number requiring intervention, such as chest tube placement, will be recorded. Significant hemoptysis will be defined as bleeding noted at the time of procedure that requires a change in the level of care (e.g. outpatient to inpatient or inpatient to ICU) or a blood transfusion. Other adverse events that are common to bronchoscopy described above in “Risks” section will be monitored and reported by the patient or nursing staff.

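### The safety outcome is labelled as that of EBUS-MFB, but the events as planned are counted over the whole session, including the inspection and needle aspiration that precede it

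*Combined protocol and SAP*

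**What the plan says.** - **Outcome.** Secondary outcomes has a single item: "Adverse event rates and safety profile of EBUS-MFB".
- **Before the forceps step.** Under Bronchoscopy, step 2 is airway inspection. Step 3 states: "Transbronchial needle aspiration from the targeted lesion will be performed using a 22 gauge aspiration needle". Step 4b sends the operator to further enlarged nodes for EBUS-TBNA when on-site evaluation (ROSE) is non-diagnostic, and ends the procedure without forceps if there are none.
- **Entry to the forceps step.** Step 4a: "in cases in which ROSE yields a specific diagnosis of nonsmall cell lung cancer, EBUS-MFB will subsequently be performed".
- **The forceps step.** Step 5 sets out how EBUS-MFB is done. It begins at 5a: "6 needle punctures will be made into the targeted lymph node using the 22 gauge aspiration needle". At 5b the forceps pass "into the targeted lymph node through the puncture site made using the 22 gauge needle using continuous endobronchial ultrasound guidance". At 5d: "8 core biopsies will be obtained from each targeted lymph node using this technique".
- **Recording.** Data Collection item 5 opens: "Adverse event rates will be documented". It then defines significant hemoptysis and how pneumothorax is documented. Item 3 lists procedure time, sedation and number of biopsies.
- **Definition and analysis.** Reportable Events counts any untoward occurrence up to 24 hours after the procedure, irrespective of relatedness, and has the investigator class each as expected or unexpected. Statistical Analysis lists adverse events among the descriptive summaries. It names no comparator, and no denominator for the event rate.

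**The concern.** The outcome names one technique, while the counting rule covers everything done in the session. A fall in oxygen saturation during sedation, or bleeding at a node that was aspirated but never reached by forceps, would enter a figure headed as the safety profile of EBUS-MFB whenever the patient went on to step 5.

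This matters because the plan describes ROSE-guided EBUS staging as standard of care, and the forceps biopsies are taken after ROSE has already given the diagnosis. A reader of the result will want to know what the forceps step adds. The Data Safety Monitoring Plan section anticipates no risk beyond that of the standard procedures, and the secondary outcome is the planned measurement that could inform that statement. Item 3 of Data Collection does not list the time at which step 5 began, so the listed fields would not allow the stages to be separated afterwards.

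**Working it through.** There is no event rate in the documents to reproduce, and the target of 20 carries no derivation. The check is mainly a tracing of the sequence, with arithmetic for illustration.

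**1. Can any patient contribute EBUS-MFB alone?** Step 5 requires a ROSE diagnosis (step 4a). ROSE requires a needle sample (step 3), and that follows inspection (step 2). So every forceps patient has had steps 2 to 4, and step 4b means some may have had aspiration at other nodes as well.

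**2. Where does EBUS-MFB begin?** The 6 punctures are the first sub-step of step 5, and the forceps use the puncture site. An event during the punctures is therefore an EBUS-MFB event by the plan's own definition. The part outside EBUS-MFB is what happens before step 5a.

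**3. Does any rule separate the two parts?** Data Collection item 5 has no stage. Reportable Events disregards relatedness and classifies by expectedness only. Statistical Analysis gives percentages. None separates them.

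**4. Size, hypothetical.** Assume all 20 enrolled patients reach step 5 and 2 have an intra-procedural event.
- Reported rate: 2/20 = 10%.
- Onset at or after step 5a: 0/20 = 0%, 1/20 = 5% or 2/20 = 10%. The planned data do not say which.
- Exact (Clopper-Pearson) 95% interval for 2/20: 1.2% to 31.7%. For 0/20 the upper limit is 16.8%.

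**5. Why one rate cannot be split.** Let a be the risk before step 5a and b the added risk from step 5a onward. Both are assumed values, and the two are taken as independent. The combined risk is c = 1 − (1 − a)(1 − b).
- a = 2%, b = 5%: c = 1 − 0.98 × 0.95 = 6.9%.
- a = 5%, b = 2%: c = 1 − 0.95 × 0.98 = 6.9%.
- With a at 1%, 2% or 5% and b at 0%, 2% or 5%, c runs from 1.0% (a = 1%, b = 0%) to 9.75% (a = b = 5%).

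The same 6.9% fits a forceps step that adds 2% and one that adds 5%.

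**6. Denominator.** Patients who stop after non-diagnostic ROSE have the needle stage only, and their number is not given. Two events among forceps patients are 2/20 = 10% of those enrolled. They are 2/14 = 14.3% if 14 reached step 5, or 2/10 = 20% if 10 did (14 and 10 are assumed). The needle-only patients are not a usable comparison group, because the ROSE result selects them.

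**The case against.** The strongest reply is that EBUS-MFB is used here as an addition to ROSE-positive EBUS-TBNA, so the rate for the whole sequence is the one that applies in practice. The study is single-arm and descriptive, and no comparison, safety threshold or causal claim depends on separating stages. With 20 patients, sampling error (1.2% to 31.7% around 2/20) is wider than the shift at issue. All of this stands. It limits the point to labelling and data capture, but it does not make the present label accurate.

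A reader might also infer more than the documents support:

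- **That the 6 punctures contaminate the forceps rate.** They are step 5a of EBUS-MFB. Counting only events from the first forceps pass would leave out an integral step and understate the rate.
- **That a procedure aborted during TBNA is charged to the forceps.** Such a patient never reaches step 5, so this cannot happen among forceps-treated patients.
- **That events are recorded only after the session.** Item 5 refers to bleeding seen during the procedure, and Reportable Events makes the investigator responsible for identifying events during it. What is missing is the stage. No case-report form is among the documents, so the gap is in what the plan requires.
- **That the secondary outcome cannot be answered.** The full-sequence rate is valid if it is labelled as such.
- **That stage of onset would establish cause.** Bleeding seen after the first forceps pass may come from the needle tract, and a pneumothorax first seen on the post-procedure x-ray cannot be assigned to a stage.

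**Conclusion.** The point holds in limited form. The figure that the plan will produce is the 24-hour event rate of sedation, inspection, EBUS-TBNA and EBUS-MFB together, and the plan labels it as the safety of EBUS-MFB. Events that begin before step 5a are counted under that label and cannot be identified later from the fields listed.

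Its size depends on rates that the documents do not give. In the hypothetical case of 2 events in 20 forceps patients, a reported 10% could correspond to anything from 0% to 10% with onset from step 5a onward. This assumes that all 20 reach step 5 and that both events occur during the procedure.

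The change is worth making because it costs little and sharpens the only secondary outcome. The combined rate remains valid under an accurate name, and neither the primary outcome nor the enrolment target is affected.

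**What to change.** 1. **Data Collection item 5.** For each event, record the stage of onset as one of three categories: before step 5a (sedation, inspection, TBNA); from step 5a onward (punctures and forceps), with a flag for onset after the first forceps pass; or first detected in recovery or later in the 24-hour window, marked as stage unattributable.
2. **Secondary outcomes.** Label the overall rate as that of EBUS-TBNA followed by EBUS-MFB.
3. **Statistical Analysis.** State the denominator of the overall rate. Among patients in whom step 5 was begun, also report events with onset from step 5a onward, and show recovery-detected events on a separate line. State that stage of onset describes timing and does not establish cause.

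The cost is one field per event, completed by staff already monitoring the procedure, plus a few lines of tabulation. No procedure, sample size or patient management changes. Some events, pneumothorax in particular, will stay unassigned.

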#### DEFINITIONS:

Central lung lesion: lesions immediately adjacent to the tracheobronchial tree accessible by biopsy using convex-probe endobronchial ultrasound and inclusive of, but not limited to, mediastinal and hilar lymphadenopathy.

Feasibility: feasibility will be defined as the ability to provide adequate specimens to perform PD-L1 testing. Any specimen in which the requested assay returns as "insufficient material to perform testing" will be deemed an "inadequate" specimen.

#### SUBJECT ENROLLMENT:

Subjects presenting to the Interventional Pulmonology service at Washington University School of Medicine in need of a bronchoscopic biopsy of their central lung lesion as part of their standard medical care, and who meet study inclusion/exclusion criteria, will be invited to participate. A total of 20 patients will be enrolled in this feasibility study. The PI will explain the study to qualified subjects prior to obtaining consent. The subject will also be given an opportunity to review and sign documentation of HIPAA compliance and authorization.

#### **Inclusion criteria:**

Patients to be included for participation in this study are:

1. Patients with central lung lesion 1cm in size or larger identified on chest CT with the intention to undergo bronchoscopic evaluation and biopsy. The decision to pursue biopsy will be made by the treating physician and agreed upon by the patient.
2. Are at least 18 years old
3. Are able to provide informed consent
4. Are not pregnant as confirmed by bHCG testing prior to procedure

#### **Exclusion criteria:**

Patients to be excluded from participation in this study are:

1. Patients who refuse to participate
2. Are less than 18 years of age
3. Are pregnant
4. Are physically unable to tolerate flexible bronchoscopy or moderate sedation as determined by the bronchoscopist
5. Are unable to provide informed consent
6. Are on anticoagulant medications and who cannot safely discontinue their medication prior to their procedure at the recommendation of their treating physician

#### INFORMED CONSENT:

Informed consent will take place in a private environment (e.g. patient exam room), free from distractions. The PI (or another member of the study team with consenting duty) will approach the subject at their standard of care clinic appointment or prior to their scheduled bronchoscopy and will explain the study to qualified subjects prior to obtaining consent. Interviews to obtain consent will not follow any stressful situation (e.g. patient being informed he/she may have cancer) and will not be conducted if patient has received any mind-altering medications or anesthesia. Patients will be assessed for their capacity to consent by the ability to show comprehension of the procedure, ask appropriate

questions, and appear properly oriented. A signed copy of all consents and the HIPAA authorization document will also be given to consenting subjects.

#### PROCEDURES:

All procedures will be performed in an outpatient bronchoscopy suite. All procedures will be performed under moderate sedation.

#### Bronchoscopy:

1. *Sedation:* Moderate sedation will be administered by the bronchoscopy team in a dedicated bronchoscopy suite. Patients will be continuously monitored throughout the procedure as per standards of care at Barnes-Jewish Hospital.
2. *Airway inspection:* When adequate sedation has been given, the bronchoscope (BF-P190, Olympus, Tokyo, Japan) will be inserted transorally into the tracheobronchial tree and a standard airway inspection will be performed.
3. *Convex-probe endobronchial ultrasound and transbronchial needle aspiration:* Following standard airway inspection, the convex-probe EBUS bronchoscope (BF-UC180F, Olympus, Tokyo, Japan) will be inserted transorally into the tracheobronchial tree and will be advanced to the targeted centrally located lesion. Transbronchial needle aspiration from the targeted lesion will be performed using a 22 gauge aspiration needle.
4. *Rapid on-site evaluation (ROSE):* Rapid on-site evaluation will be performed as per standard clinical care by a cytology team.
  - a. ROSE diagnostic: in cases in which ROSE yields a specific diagnosis of nonsmall cell lung cancer, EBUS-MFB will subsequently be performed.
  - b. ROSE non-diagnostic: in cases in which ROSE does not yield a specific diagnosis, additional lymph nodes that are pathologically enlarged as defined above will be targeted for EBUS-TBNA
    - i. If no additional lymph nodes are pathologically enlarged, the procedure will be terminated and EBUS-MFB will not be performed
5. *EBUS-miniforceps biopsy:* following the diagnosis of nonsmall cell lung cancer using ROSE, EBUS-MFB will be performed in the following manner:
  - a. With the EBUS bronchoscope positioned at the targeted lymph node station, 6 needle punctures will be made into the targeted lymph node using the 22 gauge aspiration needle through the EBUS bronchoscope using continuous endobronchial ultrasound guidance.
  - b. The 22 gauge aspiration needle will then be removed and 1mm miniforceps (Boston Scientific), will be passed through the working channel of the EBUS-bronchoscope into the targeted lymph node through the puncture site made using the 22 gauge needle using continuous endobronchial ultrasound guidance.
  - c. The miniforceps will be used to obtain a core biopsy of the targeted lymph node using continuous endobronchial ultrasound guidance and will be withdrawn from the EBUS bronchoscope.

- d. 8 core biopsies will be obtained from each targeted lymph node using this technique, with each core biopsy specimen placed in formalin for PD-L1 testing.
6. Management of complications: the major complications of bronchoscopic biopsy include pneumothorax and bleeding:
  - a. Pneumothorax: a post procedure chest x ray will be performed following the bronchoscopy. Should a pneumothorax be present, it will be managed by either observation and follow up chest x-ray or by tube thoracostomy at the discretion of the bronchoscopist.
  - b. Bleeding: intra procedural bleeding will be managed using local tamponade, iced saline lavage or mechanical occlusion at the discretion of the bronchoscopist.

Post-bronchoscopy:

1. *Chest x-ray:* A routine portable chest x-ray will be performed on all patients following bronchoscopy as per standard clinical practice at Barnes-Jewish Hospital/Washington University School of Medicine to assess for pneumothorax.
2. *Recovery:* Patients will be recovered in a dedicated post-procedure area as per standard care at Barnes-Jewish Hospital/Washington University School of Medicine

Laboratory Analysis:

1. Formalin placed specimens will be sent for PD-L1 testing using the assay specific for nivolumab.

RISKS OF PROCEDURES:

The greatest risks from bronchoscopy are related to moderate or deep sedation and the very act of passing a bronchoscope into the airway. To mitigate risks of bronchoscopy all patients will be monitored by a nurse and a respiratory therapist during the procedure. In addition, oxygen saturation (using pulse oximetry) respiratory rate, blood pressure, ECG, and heart rate will be continuously monitored. Patients will not be released until they are fully awake and medically stable.

The risks associated with bronchoscopy are collapsed lung, breathing difficulty, vocal cord spasm, vomiting, dizziness, bronchial spasm, infection, low blood oxygen, heart attack and bleeding from biopsied site. The occurrence of these risks is extremely low. The measures to mitigate the risks are the same as for all bronchoscopy. To assess for pneumothorax following the bronchoscopy, patients will get a portable chest X-ray. To minimize the chance of bleeding, all patients will be questioned about tendency to bleed prior to bronchoscopy as per standard care. Anticoagulation with antiplatelet agents will be held according to guideline recommendations for that drug. If bleeding occurs, patients will be treated with direct pressure, local instillation of epinephrine or electrocautery. Patients with lung disease may receive bronchodilators prior to bronchoscopy at the discretion of the performing bronchoscopist. There is no way to reduce the minimal risk of infection due to bronchoscopy since the scope must go through the oropharynx. Patients are given supplemental oxygen and their oxygen level is continuously monitored using pulse oximetry. Patients ECG, heart rate, blood pressure, and blood oxygen are continuously monitored by a nurse, respiratory therapist and physician during the

procedure. If there is any sign of a worsening in status, such as elevated heart rate, low oxygen, or ECG changes, the procedure will be aborted.

